1. INTRODUCTION

Prostate cancer (PCa) is the second most common cancer in men, primarily affecting older men. The standard treatment for recurrent and metastatic Pca is ADT. It is also standard of care for men with intermediate or high risk localized prostate cancer who plan to get radiation to receive ADT in the neoadjuvant and adjuvant setting. It is well established that ADT causes muscle weakness and wasting, osteoporosis, and fatigue. Our preliminary data suggests that older men on ADT have significant physical performance deficits, functional impairments, and falls at higher rates than men in the general geriatrics population. HMB is a leucine metabolite which has been shown to decrease the rate of muscle protein breakdown. When given with arginine and lysine or glutamine, HMB has been shown to improve strength, fat-free mass and function in the general geriatrics population who are prone to sarcopenia. Use of HMB and/or amino acid supplementation in older men with PCa starting on ADT has not been reported. We will prospectively: 1) measure the change in body composition, strength, physical performance, and falls in older men with PCa starting on ADT, comparing those who receive HMB + AG versus those who do not, 2) evaluate the use of MRI and muscle biopsy to identify changes in muscle composition and muscle fatiguability that are known to occur in this patient population. We will test the hypothesis that HMB + AG can reduce the adverse change in body composition and strength/muscle fatiguability that occur when older men with PCa are started on ADT. With data obtained

in this study, a larger randomized study will be designed to compare interventions aimed at minimizing the adverse affects that occur with ADT initiation.

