4. SELECTION OF PATIENTS

Prostate cancer patients under the care of an MCW Cancer Center physician will be eligible to participate.

Inclusion criteria:

- 1) Histologically confirmed adenocarcinoma of the prostate
- 2) Age 60 years or older
- 3) Patients with asymptomatic or minimally symptomatic PCa for which they are about to start androgen deprivation therapy (ADT) per provider recommendation
 - Asymptomatic or minimally symptomatic (as judged by treating physician) metastases allowed
 - Men receiving ADT for localized prostate cancer are allowed
- 4) Patient able to give informed consent.

Exclusion criteria:

- 1) Patient already on ADT
- 2) Patients who are visiting clinic for a second opinion only
- 3) Patients with a diagnosis of dementia
- 4) Patients with a diagnosis of a neuromuscular disorder (i.e. multiple sclerosis)

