5. STUDY DESIGN AND STATISTICAL CONSIDERATIONS

Objective 1: Prospectively measure the change in body composition, strength, physical performance measures, and falls in older men with PCa starting on ADT, comparing those who receive HMB + AG versus those who do not.

Rationale: Older men with prostate cancer who start on ADT experience clinically significant muscle loss and weakness as a result of treatment, likely contributing to increase risk of falls and fractures and decreased quality of life. Treatments are needed which counteract the loss of muscle mass and strength caused by ADT. HMB + AG, which decreases protein/muscle breakdown, has been shown to increase lean muscle mass and strength in elderly men and women. It seems plausible that HMB + AG could counteract the muscle loss and weakness that men experience as a result of ADT; effectiveness of HMB + AG in men with prostate cancer starting ADT has not been studied.

Experimental Design: We will conduct a prospective cohort pilot study of men age 60 and older with Pca who are about to start ADT. All men will be followed prospectively for 3 months from time of initiation of ADT. Men will be randomized to receive HMB + AG versus no supplement (Figure 2). Assessments will be performed at baseline (before or within 2 weeks of starting ADT) and 3 months (Table 2). Adherence to HMB will be assessed by patient diaries. Functional assessments and basic strength measurements will be performed at baseline and 3 months. These will include the Short Physical Performance Battery (SPPB), a validated measure which evaluates balance, gait, strength, and endurance and has been shown to predictive of morbidity and mortality at 4 years. Hand dynamometer (grip strength, predictive of morbidity and mortality on older patients) and 3 month history of falls will also be assessed. Physical activity will be measured with tri-axial accelerometers (Actigraph, Pensacola FL) that persons will wear on a belt around the waist for 7-days. This has been used previously in men with prostate cancer. Body composition will be measured with Dual-emission X-ray absorptiometry (DXA) scan at baseline and 3 months. Muscle strength will be measured with non-magnetic force transducers and composition will be measured with MRI at baseline and 3 months (SA2). Muscle biopsies will be done on a subset of patients who agree to the procedure (SA3).

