Setting: The patients will be recruited from Oncology and Urology clinics at Froedtert Hospital. PCa patients in the clinics who consent to participate in this study will do physical performance testing at each assessment. A trained research assistant (RA) will administer testing and enter data into a secure database. Serious adverse events and study progress for this investigator initiated trial will be monitored by [name] per NCI CCSG guidelines. Recruitment: Based on the number of patients currently seen in these clinics, approximately 2-3 patients will be seen a week who are eligible for this study. A total of 80 patients (40 in each arm) will be enrolled in this pilot study.

[figure not shown]

Table 2: Measures performed over time per group						
	Baseline			3 months		
	SPPB			SPPB		
	HD	MRI	Biopsy	HD	MRI	Biopsy
	falls		. ,	falls		
Control	Χ	X*	X*	Χ	X*	X*
HMB	Χ	X*	X*	Χ	X*	X*

SPPB: Short Physical Performance Battery; HD: hand dynamometer:

* MRI and Biopsy to be done on subset of sample

Data Analysis:

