Study design: The trial will be conducted in two phases, with 40 patients recruited for both phases. After the first 40 patients have been evaluated, a two-sample one-sided t-test comparing the mean lean body mass loss will be conducted. If the one-sided p-value is equal or less than 0.0088, the trial will be stopped for efficacy. If the p-value exceeds 0.3, the trial will be stopped for futility. In all other cases the trial will proceed to the next phase. At the end of the second phase a two-sample one-sided t-test comparing the mean lean body mass loss in the two groups will be conducted at a 5% significance level. Randomization: Randomization will be stratified by exercise status to ensure almost equal representation of both strata in both treatment groups. A block-size of 8 will be used, that is among each 8 consecutive patients exactly 4 will receive each treatment. Due to the presence of strata this blocking will not ensure exactly equal group size, however compared to unblocked randomization it will keep the group-size difference lower. Sample size considerations: The study was powered to detect a smaller lean body mass loss by 0.8 kg in the treated group using a one-sided twosample t-test at a 5% significance level. This effect size corresponds to approximately 50% of the expected lean body mass loss in the control group, and is similar to the effect achieved by an exercise intervention.³⁸ Based on literature review the standard deviation of within-person lean body mass change was assumed to be 1.4kg.^{38,39} The following table shows the power of the study and the probability of early stopping for efficacy/futility with the planned total sample size of 40 subjects per group and one interim analysis after 20 patients. The values are based on 10,000 simulation runs.

Difference in lean body	Probability of early stopping	Probability of early stopping	Overall
mass loss, kg	for efficacy	for futility	power
0	0.9%	70.3%	4.7%
0.4	6.5%	35.4%	33.7%
0.8	26.4%	10%	78.0%
1.2	59.5%	1.5%	97.5%
1.6	86.8%	0.1%	99.8%

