Statistical analysis plan: As described in the study design, the primary outcome of within-person lean body mass change will be analyzed using a one-sided two-sample t-test. This test will be conducted at a 0.88% significance level after 20 patients have been evaluated in both arms, and, if the study proceeds to the end, at a 5% significance level after 40 patients have been evaluated in both arms. The secondary outcomes will be evaluated using a t-test or Wilcoxon rank-sum test as appropriate.

Anticipated Results/Interpretation: We anticipate that body composition will be better preserved in the supplemented group after initiation of ADT. In addition, we expect less functional limitations to mobility in the supplemented group as indicated by greater physical activity as measured by accelerometry. Further we expect physical activity to be positively related to muscle strength and endurance.

Objective 2: Prospectively measure the fatiguability and muscle size using MRI/Phosphorus MRI spectroscopy (³¹P-MRS) in older men with PCa starting on ADT, comparing those who receive HMB + AG versus those who do not.

Rationale: Fatigue is highly prevalent in men with PCa undergoing ADT and can affect QOL. Muscle fatigue could be due decreased oxidative capacity as a primary or secondary effect of the cancer or its treatment. Fatigue could also result from muscle weakness or loss of strength. The later could occur when a smaller amount of muscle has to accomplish the same amount of work as that of a larger amount. 31P- MRS is a non invasive *in vivo* technique which can be used to study phosphorus energy metabolites in conscious humans during exercise. As such, it can help to delineate the causes of muscle fatigue in PCa with ADT. We expect both to play a role. HMB + AG has been shown to increase muscle strength in older patients. It stands to reason that muscle strength and fatiguability would improve in older men with prostate cancer on ADT who receive HMB + AG.

Experimental Design: A subset of consenting patients (estimated 20 per group) will be assessed at time increments as outlined above. Cross sectional area of quadriceps muscle will be assessed using MRI. Muscle fatiguability will be measured as time to task failure (i.e. endurance and PCr recovery) using 31P-MRS at baseline and 3 months.

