Data Anlaysis: Exploratory MRI studies will be conducted on the first 40 consenting patients. This sample size will provide an 80% power to detect large effects with effect size of 0.9 or above at a two-sided 5% significance level.

Anticipated Results/Interpretation: We expect lean cross sectional area and therefore strength to be preserved or enhance in the HMG+AG group. We also expect endurance and muscle oxidative capacity to be preserved or enhanced in the HMG+AG group.

Objective 3: Prospectively analyze muscle fiber cross sectional area and fiber type using muscle biopsy in a subset of men with PCa starting ADT, comparing those who receive HMB + AG versus those who do not.

Rationale: Studies in older patients indicate that HMB, when given with amino acids, helps to maintain protein synthesis and slow muscle breakdown. ADT is known to cause accelerated loss of lean muscle mass. HMB + AG, when given to men starting androgen deprivation therapy, may prevent loss of lean muscle mass. Biopsy of muscle will definitively show cross sectional area and fiber type (fast versus slow) in this patient population. A better understanding of changes in fiber type will clarify the pathophysiology behind ADT toxicity and the potential mechanism of action of HMB + AG.

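### Endurance and PCr recovery would, by inference, be compared by an unadjusted two-sample test, giving up precision available from the baseline value and the exercise stratum

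*Combined protocol and SAP*

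**What the plan says.** Section 5, Objective 1, Statistical analysis plan gives the primary outcome a one-sided two-sample t-test on within-person change. It then covers everything else in one sentence: "The secondary outcomes will be evaluated using a t-test or Wilcoxon rank-sum test as appropriate".

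Objective 2, Experimental Design defines the outcomes at issue: "Muscle fatiguability will be measured as time to task failure (i.e. endurance and PCr recovery) using 31P-MRS at baseline and 3 months". Its data analysis paragraph says "Exploratory MRI studies will be conducted on the first 40 consenting patients" and claims 80% power for an effect size of 0.9 at a two-sided 5% level. The expected number is 20 per group. No test or model is named there.

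On allocation, Section 5 says: "Randomization will be stratified by exercise status to ensure almost equal representation of both strata in both treatment groups". Exercise status is the only stratification factor. No covariate, stratified test or regression model appears anywhere in the plan.

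**The concern.** Two variables that could sharpen the comparison will already be in hand. The baseline value of each outcome is measured, and exercise status must be known to randomize. An unadjusted test uses neither as a covariate.

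The plan also leaves open which quantity is tested. Within-person change is specified for the primary outcome only. A change score uses baseline by subtraction, with a fixed coefficient of 1; a comparison of 3-month values does not use it at all. With about 20 men per arm the choice matters, and Section 3 says the data are meant to help design a larger randomized study.

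**Working it through.** **Inputs from the documents:** 20 per arm, effect size 0.9, two-sided 5% (Objective 2). **Assumed, because the documents give no value:** the baseline-change correlation, the pre-post correlation r, and the size of any difference between exercise strata. Normal outcomes and no dropout are also assumed.

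**1. The plan's own figure.** For a two-sample t-test the noncentrality is 0.9 × sqrt(20/2) = 2.85 on 38 df. Power is 79.2% (81.2% by the normal approximation). The stated 80% is reproduced, and it matches an unadjusted comparison. For a Wilcoxon test with normal data (relative efficiency 0.955), power is about 77%.

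**2. If 0.9 is in SDs of change.** ANCOVA on baseline and stratum has 38 - 2 = 36 residual df. If baseline correlates c with change, the residual SD is sqrt(1 - c²):

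- c = -0.3: 0.9/sqrt(1 - 0.09) = 0.943
- c = -0.5: 0.9/sqrt(1 - 0.25) = 1.039

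The power figures below come from simulation, which allows for chance imbalance in baseline. The stratum is taken as not prognostic.

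| Baseline-change correlation | Change-score t-test | ANCOVA, baseline + stratum |
|---|---|---|
| 0 | 79% | about 78% |
| -0.3 | 79% | about 82% |
| -0.5 | 79% | about 88% |

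With equal variances before and after, c = -sqrt((1 - r)/2). So c = -0.5 corresponds to r = 1 - 2 × 0.25 = 0.5, and c = -0.3 to r = 1 - 2 × 0.09 = 0.82. Neither is an unusual value.

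**3. If 0.9 is in SDs of the 3-month value.** The SD of change is then sqrt(2(1 - r)) and the ANCOVA residual SD is sqrt(1 - r²). ANCOVA here is on baseline only, with 37 df (noncentral t).

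| r | t-test, 3-month values | t-test, change | ANCOVA |
|---|---|---|---|
| 0.3 | 79.2% | 65.0% | 82.8% |
| 0.5 | 79.2% | 79.2% | 89.3% |
| 0.7 | 79.2% | 94.7% | 97.3% |

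The choice between 3-month value and change, which the plan does not make, moves power by about 14 to 16 points at r = 0.3 and 0.7. ANCOVA is above both tests in every row.

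**4. Exercise stratum.** Assume two equal strata, balanced between arms. If they differ by 0.5 SD, the SD seen by the t-test is sqrt(1 + 0.25 × 0.5²) = 1.03. By simulation its power is about 77% and its type I error about 4.5%. At 1.0 SD these are about 72% and 3.0%. Including the stratum restores about 79% and 5%. Leaving it out is therefore conservative.

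**The case against.** **A legitimate choice.** An unadjusted two-sample test in a 40-man subset that the plan calls exploratory is valid. A reader might infer that the comparison is biased, or that the 80% power is wrong. Neither follows: randomization protects the unadjusted tests, and step 1 reproduces the figure.

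**Baseline may not be wholly unused.** The objectives speak of change and loss, so a change score may be intended. That stands, and it is why the point is limited to baseline as a covariate. Against a change score the gain at a correlation of -0.3 is only about 3 points.

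**Inference and scope.** The sentence on secondary outcomes sits under Objective 1, and the plan does not expressly list endurance or PCr recovery as secondary outcomes. It is nonetheless the only sentence that could cover them. The other secondary outcomes fall under it too, so the same wording could be considered for them.

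**Radiotherapy.** A reader might infer that radiotherapy must also be adjusted for. The Introduction describes ADT as standard for men with intermediate or high risk "localized prostate cancer who plan to get radiation to receive ADT in the neoadjuvant and adjuvant setting", Section 4 says "Men receiving ADT for localized prostate cancer are allowed", and the pilot in Section 2 saw endurance fall from 556 to 391 s after radiotherapy. But that pilot had 12 irradiated men, tested the ankle dorsiflexors over 6 weeks, and its controls rose from 616 to 753 s. No passage says how many participants would be irradiated between baseline and 3 months. Absence from Table 2 shows little, since that table omits DXA as well. The documents do not support a radiotherapy covariate.

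**Skewed times.** Linear ANCOVA can lose to Wilcoxon. One set of simulations used lognormal changes (log-SD 0.8) and an assumed 0.56 SD radiotherapy effect in 10-50% of men. Wilcoxon had 96-97% power, linear ANCOVA 79-80% and ANCOVA on ranks 96-97%. This stands, so a rank option should be kept. A rule that switches to ranks when residual skewness exceeds 1 looks attractive but reached only about 91-94% with lognormal changes, so it is not recommended.

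**Conclusion.** The point holds as a modest loss of precision and a gap in specification. By inference, endurance and PCr recovery are compared without baseline as a covariate and without the stratum, and the tested quantity is not stated.

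For an effect of 0.9 SD of change, adjustment moves power from 79% to about 82% or 88% at baseline-change correlations of -0.3 or -0.5. Against 3-month values it moves power from 79% to about 83%, 89% or 97% at r = 0.3, 0.5 or 0.7. If neither covariate is prognostic, power falls to about 78%. All of these rest on assumed correlations, 20 evaluable men per arm and normal outcomes. This is worth considering; it is not a defect that undermines the trial.

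**What to change.** Under Objective 2, state that endurance and PCr recovery will each be analysed by ANCOVA with treatment, baseline value and exercise stratum. The outcome may be the 3-month value or the change: with baseline in the linear model the treatment estimate is the same, so the ambiguity disappears.

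If a rank-based analysis is wanted in place of the Wilcoxon test, fit the same model on ranks. Choose it, and the quantity to be ranked, before the data are seen.

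The cost is SAP wording and two of 38 degrees of freedom, or about 1-2 points of power if neither covariate is prognostic. Ranks cost roughly 2 points when changes are normal. No additional data are needed.

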3. HYPOTHESIS AND OBJECTIVES

Use of HMB and/or amino acid supplementation in older men with PCa starting on ADT has not been reported. We will prospectively: 1) measure the change in body composition, strength, physical performance, and falls in older men with PCa starting on ADT, comparing those who receive HMB + AG versus those who do not, 2) evaluate the use of MRI and muscle biopsy to identify changes in muscle composition and muscle fatiguability that are known to occur in this patient population. We will test the hypothesis that HMB + AG can reduce the adverse change in body composition and strength/muscle fatiguability that occur when older men with Pca are started on ADT. With data obtained in this study, a larger randomized study will be designed to

compare interventions aimed at minimizing the adverse affects that occur with ADT initiation.

Objectives:

- 1. Prospectively measure the change in body composition, strength, physical performance measures, and falls in older men with PCa starting on ADT, comparing those who receive HMB + AG versus those who do not.
 - Hypothesis: Men who are randomized to receive HMB + AG will experience less lean body mass loss, less decrease in strength, less decline in physical performance, and fewer falls than those who do not receive HMB + AG.
- 2. Prospectively measure the fatiguability and muscle size using MRI/Phosphorus MRI spectroscopy (³¹P-MRS) in older men with PCa starting on ADT, comparing those who receive HMB + AG versus those who do not.
 - Hypothesis: Men who are randomized to receive HMB + AG will experience less muscle fatigue and less loss of muscle cross-sectional area than those who do not receive HMB + AG.
- 3. Prospectively analyze muscle fiber cross sectional area and fiber type using muscle biopsy in a subset of men with PCa starting ADT, comparing those who receive HMB + AG versus those who do not. Hypothesis: Men who are randomized to receive HMB+ AG will experience less loss of cross-sectional area and less loss of fast type II fibers than those who do not receive HMB + AG.

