Experimental Design: A subset of patients will undergo muscle biopsy (vastus lateralis) at baseline and 3 months. We will compare pre-ADT versus post-ADT muscle biopsy for fiber type composition and fiber type cross sectional area. Muscle fiber type histochemical staining will be done as follows: 1) Biopsies will be quick frozen in isopentane cooled with liquid nitrogen, 2) Store frozen pre sample at -80C until get individual's post sample, 3) Cut 10 micron cross sections of pre and post and collect sections on same slide; process together in same incubation medium to prevent variation in day to day composition of the incubation conditions, 4) Incubate slides for histochemical myofibrillar ATPase activity using acid-preincubation and alkaline-preincubation to accentuate fast and slow fiber subtypes, 40 5) Based on muscle fiber staining intensities, quantified with MetaMorph computerized optical density readings, segregate fibers into fast and slow fiber types and determine the percentages of each type. For each fiber, measure its cross sectional area using MetaMorph digitizing planimetry. A separate consent form will be provided to consent for this procedure. We will compare those who receive HMB + AG to those who do not.

Data Analysis: Exploratory muscle biopsies will be conducted on the first 10 consenting patients. This sample size will provide an 80% power to detect large effects with effect size of 0.9 or above at a two-sided 5% significance level.

Anticipated Results/Interpretation: The percentage of fast fibers will decrease post ADT. Slow fibers will transform from slow to fast (shift in gene expression from slow myosin to fast myosin). The cross sectional areas of fast and slow fibers will decrease post ADT. ADT causes decreased synthesis of contractile proteins so muscle fibers atrophy. The post ADT shift in slow to fast fibers and fiber atrophy will cause the individual to

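### Objective 3 (muscle biopsy) claims 80% power at effect size 0.9 with 10 patients; its between-arm comparison has about 24%

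*Combined protocol and SAP*

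**What the plan says.** The Data Analysis paragraph of Objective 3 in Section 5 states: "Exploratory muscle biopsies will be conducted on the first 10 consenting patients. This sample size will provide an 80% power to detect large effects". The sentence goes on to put the effect at 0.9 or more, tested two-sided at 5%. It names neither the comparison nor the test.

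Section 5, Objective 2, Data Analysis uses the same power sentence for four times as many patients: "Exploratory MRI studies will be conducted on the first 40 consenting patients. This sample size will provide an 80% power to detect large effects". The Objective 2 design estimates 20 patients per group.

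The question put to the biopsies is mainly a comparison of arms. The Objective 3 hypothesis in Section 3 is that men randomised to the supplement "will experience less loss of cross-sectional area and less loss of fast type II fibers than those who do not receive HMB + AG". The Objective 3 Experimental Design ends: "We will compare those who receive HMB + AG to those who do not". Earlier, the same paragraph also names a within-person comparison: "We will compare pre-ADT versus post-ADT muscle biopsy for fiber type composition and fiber type cross sectional area".

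**The concern.** Objectives 2 and 3 are both framed as comparisons of the two arms. For one type of comparison, the same effect size, significance level and power cannot hold at both 40 and 10 patients, so at least one of the two sentences must be wrong.

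What is at stake is how the biopsy result is read. Someone who trusts 80% power would take a null between-arm result as evidence against a large supplement effect on muscle fibres. Section 3 says the study's data will be used to design a larger randomised trial, so that misreading could carry forward.

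**Working it through.** **Inputs.** From Objective 3, Data Analysis: 10 patients in total, effect size d = 0.9, two-sided alpha 0.05, stated power 80%. From Objective 2: 40 patients, about 20 per group. Assumptions: d is the standardised between-arm difference in within-person change, changes are normal with equal variances, and all pairs are evaluable. No split of the 10 biopsied patients is fixed; 5:5 is the most favourable.

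**Formula.** For arms of n1 and n2, the two-sample t-test has df = n1 + n2 − 2 and noncentrality λ = d × √(n1·n2/(n1 + n2)). Power is the probability that a noncentral t variable with that df and λ falls beyond ± the 97.5% point of t.

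**Step 1: the MRI sentence (20:20).** λ = 0.9 × √(400/40) = 0.9 × √10 = 2.85, df = 38. Power is 79.2% by t-test and 81.2% by normal approximation. The stated 80% is reproduced for 40 patients.

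**Step 2: the biopsy sentence, between arms (5:5).** λ = 0.9 × √(25/10) = 0.9 × √2.5 = 1.42, df = 8. Power is 24.1%; a simulation of 200,000 trials gave 24.2%. The normal approximation gives 29.6%.

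**Step 3: other between-arm cases at d = 0.9, two-sided 5%.**

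| Case | Power | Difference detectable with 80% power |
|---|---|---|
| 5:5, t-test | 24.1% | 2.02 |
| 4:6, t-test | 23.4% | 2.07 |
| 3:7, t-test | 21.0% | 2.21 |
| 4:4 (8 evaluable pairs), t-test | 19.0% | 2.38 |
| 5:5, exact rank-sum (simulated) | about 17% | not computed |
| 10:10, if 10 meant per arm | 47.8% | not computed |
| 20:20, t-test | 79.2% | 0.91 |

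The rank-sum row is included because the Objective 1 analysis plan says "The secondary outcomes will be evaluated using a t-test or Wilcoxon rank-sum test as appropriate". With 5:5 the exact test has an attained size of only 3.2%. At d = 0.9, 80% power needs about 20 to 21 patients per arm (79.2% at 20, 81.2% at 21).

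**Step 4: the pre/post comparison, pooled over all 10 patients.** λ = 0.9 × √10 = 2.85, the same as for 20:20. The normal approximation therefore again gives 81.2%. The paired t-test has only df = 9 and gives 71.7%, with 80% power at 1.00.

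**Step 5: precision.** The approximate 95% confidence interval half-width for the between-arm difference, in SD units, is the 97.5% point of t times √(1/n1 + 1/n2). At 5:5 it is 2.306 × √(2/5) = 1.46. At 20:20 it is 2.024 × √(2/20) = 0.64.

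**The case against.** The strongest reply is that the power sentence names no comparison, and that the design paragraph mentions the pre/post comparison before the between-arm one. On the pre/post reading the stated figure is close: 81.2% by normal approximation, 71.7% by paired t-test. This could be where the 80% comes from. It does not rescue the sentence. The objective, its hypothesis and the last sentence of the design paragraph all concern the difference between arms, and a change pooled over arms says nothing about the supplement. The t-test figure for pre/post also falls about 8 points short.

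A second reply is that effect size is undefined. If it were scaled by the baseline SD rather than the SD of change, 5:5 would reach 80% at a pre/post correlation of about 0.90. The check: 0.9/2.02 = 0.445, and with equal variances √(2(1 − r)) = 0.445 gives r of about 0.90. The protocol gives no correlation, so this is possible but unsupported. It does mean that the 24% rests on the usual definition.

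Third, the rank-sum figure carries over a rule written for secondary outcomes under Objective 1. That is fair, and the conclusion does not need it.

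Finally, the biopsies are optional and exploratory, no decision rule depends on them, and no plan is stated to treat a null result as proof of no effect. This limits the consequence but does not make the stated power true.

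**Conclusion.** The power claim is wrong for the comparison that Objective 3 names. With 10 patients the between-arm power at 0.9 is at most about 24%, against the stated 80%; a true effect of that size would be missed about three times in four. The detectable difference is about 2.0 rather than 0.9. These figures assume a two-sided 5% t-test, a 5:5 split, all pairs evaluable, and effect size standardised by the SD of change. Departing from the even split or losing pairs lowers the power.

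The identical wording under Objective 2 is consistent with the sentence having been carried over, but the documents do not show this. The correction should be made. It does not touch the primary lean body mass analysis, the interim rule or the planned patient numbers.

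**What to change.** Replace the power sentence under Objective 3, Data Analysis, with wording such as:

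> *With 10 patients (at best 5 per arm), the between-arm comparison has at most about 24% power at a standardised difference of 0.9 in within-person change, and 80% power only at about 2.0 (two-sided 5% t-test). Biopsy results are exploratory and will be reported as estimates with confidence intervals.*

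If the sponsor meant the pre/post comparison, the text should say so and give that figure separately: about 72% at 0.9 by paired t-test on 10 pairs, pooled over arms. The commitment to confidence intervals goes slightly beyond correcting the number, but it suits so small a subset.

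The cost is one sentence of protocol wording and a less favourable figure. The size and selection of the biopsy subset and the primary analysis stay as they are.
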